7 SAFETY ASSESSMENTS

7.1 Adverse Events and Serious Adverse Events

The possible adverse events such as 1) reporting suicidal ideation; 2) discomfort with the PMP-I program content and/or evaluation procedures, and 3) risk of a breach of confidentiality of the collected data and/or by program personnel, and severe adverse events such as 1) suicide attempts and other events that involve hospitalization, disability, and/or death, will be reported in writing to the NIMH Program Officer according to pre-determined expectations and timeframes with the NIMH policy (<https://www.nimh.nih.gov/funding/clinical-research/nimh-reportable-events-policy.shtml>).

The PI will be responsible for the overall trial oversight in the community and safety of participants in the trial and will review all possible study-related and not-related adverse events. Field supervisors will also be responsible for describing and adhering to the procedures for identifying, monitoring, and reporting reportable events.

Adverse events: All study participants will be monitored closely daily by the field supervisors under the PI's supervision throughout the study period. Field supervisors will request study participants and their family members to immediately report any unanticipated adverse events in their family, such as 1) reporting suicidal ideation; 2) discomfort with the PMP-I program content and/or evaluation procedures, and 3) risk of a breach of confidentiality, of the collected data and/or by program personnel to field supervisor or PI directly. Field supervisors will immediately report details of such adverse events to PI. The PI will be responsible for summarizing all adverse events that are deemed expected and/or unrelated to the study in the annual progress report submitted to the UMass Amherst IRB, ISM, and NIMH Program Officer by secure email.

Serious adverse events: All study participants will be monitored closely daily by the field supervisors under the PI's supervision throughout the study period. Field supervisors will request study participants and their family members to report any unanticipated serious adverse event in their family, such as suicide attempts and other events that involve hospitalization, disability, and/or death, to the field supervisors or PI. Field supervisors will immediately report details of such adverse events to the PI. The PI will be responsible for

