7.3 Potential Risks and Mitigation Strategies

We do not anticipate any significant risks due to participation in research-related activities, based on our previous pilot intervention experience with similar mental health outcomes in the same population.

First, RA will remind each participant that if they perceive any question to be too personal, they can choose not to respond. Participants may feel hesitant to answer some of the questions regarding depression and suicidal ideation. In such cases, participants are free to skip such questions or are free to withdraw from participating in the study overall. If participants feel upset during or after completing the survey or find that some questions or aspects of the study triggered distress, the RA will immediately contact the PI. The PI will then immediately assist participants (in their native Nepali language) and help them to connect with mental health support services in coordination with the field supervisor. The RA will also provide them with contact information for emergency and other mental health support available locally but independent of the study.

Second, the field-team will be trained to recognize potential risks that require immediate reporting, such as suicidal ideation. If any participants respond “yes” to a questionnaire item that measures suicidal ideation or develops suicidal ideation during the intervention implementation phase, the RA will immediately contact the PI. The PI will then immediately assist participants (in their native Nepali language) and help them connect to mental health support services available in the area in coordination with the field supervisor. The field supervisor will provide the necessary support to them for setting up their appointment with primary health care providers if needed. The field supervisor will also make a follow-up home visit to monitor their mental health condition, as necessary.

Finally, all participants will be asked to contact the PI directly if they have any health concerns and/or need help during the intervention implementation phase. We would like to identify field supervisors as an alternative contact person for participants and research assistants if the Principal Investigator (PI) is busy or unavailable, for whatever reason

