10.1.5 Hair samples collection: Trained RAs will follow standard procedures mentioned in the “Training Manual for Research Assistant” to collect hair samples of study participants for the stress biomarker measurement. Hair samples will be cut from the posterior vertex of the scalp, carefully placed in aluminum foil, and stored at room temperature until delivery to [name] laboratory at the University of Massachusetts Amherst. Each sample will be cut to a length of 3 cm (if available) from the root (scalp) end and then processed into the [name] laboratory. Briefly, cut samples will be washed twice in 1 ml of isopropanol to remove external contaminants, including cortisol deposited on the outside of the hair shaft from sweat and sebum. After drying overnight, samples will be ground to be fine powder using a bead mill. 1.5 ml of methanol will be added to each sample, after which the samples will be subjected to slow rotation for 18-24 hours to extract the cortisol. 1.0 ml of the extract will be transferred to a clean tube, dried down using a vacuum evaporator, and then reconstituted in 0.25 ml of assay buffer. Reconstituted extracts will be spin-filtered to remove any residual particulate matter and then frozen at -20C for later assay. The cortisol content of each sample will be analyzed in duplicate along with standards and quality controls using the Arbor Assays commercial ELISA kit. Finally, the assay readout will be converted to pg cortisol per mg hair weight.

10.1.6 Confidentiality of participants’ information and record: All interviews will be conducted with the utmost privacy and confidentiality. Each interested adult participant in the family will be interviewed individually, in a private place where they feel comfortable, by our trained community RAs who have worked with the PI in previous intervention studies. The RAs will ensure audio and visual privacy at these sites and ensure data confidentiality. The RAs will assure each participant that their information will be kept confidential and not shared with anybody, including family members, in any context. Moreover, community interventionists will present the PMP-I interventions in family settings welcoming the participation of all interested family members, including parents

and young (<18 years) and old children (aged 18 years and above), without revealing individual participant's data and mental health status.

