11.3 Participant Confidentiality

All interviews will be conducted with the utmost privacy and confidentiality. Each interested adult participant in the family will be interviewed individually, in a private place where they feel comfortable, by our trained community RAs who have worked with the PI in previous intervention studies. The RA will ensure audio and visual privacy at these sites and ensure data confidentiality. The RA will assure each participant that their information will be kept confidential and not shared with anybody, including family members, in any context. Moreover, we will present our interventions in family settings welcoming the participation of all interested family members, including parents and young (<18 years) and old children (aged 18 years and above), without revealing individual participant's data and mental health status.

Furthermore, the RA will explain the confidentiality procedure in detail before

collecting any data. The RA will share the following procedures to maintain subject privacy: we will use a numeric code in place of names in all records to ensure confidentiality. The survey materials will be stored in a locked cabinet in the PI's office. Only the PI will have access to the cabinet's key. Data entry will be performed on the PI's office computer (encrypted and password protected) under the full supervision of the PI. All original data will be kept in Box, a secure, networked UMass Amherst data storage system. Study folders will only be accessible by the PI and through the secure on-campus network.

De-identified data sets will be used for statistical analyses. Summary data and analysis results will be stored on the PI's UMass office computer or the Box network. The PI herself will do data analysis and documentation. Data will only be presented in aggregate form in manuscripts or conference abstracts, and no individual respondent will be identified. The questionnaires, transcriptions, and field notes will be kept separate from identifying informed consent and ID information. The master list of participants will be kept under a locked cabinet with access limited to the PI.

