11.4 Confidentiality Limits

We will keep all information from participants confidential. There are certain exceptions to this rule, as permitted by law and professional ethics. Our experience is that these exceptions will arise infrequently. They will include: a) We may disclose confidential information when we judge that there is a strong possibility of serious harm being inflicted by a participant on another person or themselves, and we are unable to develop a plan with the participant to ensure safety; b) Should a participant disclose information relating to probable child abuse, elder abuse, or abuse of a vulnerable adult (for example, someone who is developmentally disabled or mentally ill, or who has a disabling illness), we may be required to notify state authorities.

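### The confidentiality assurance that RAs must give (10.1.6, 11.3) allows no exception, yet section 11.4 sets out two, and none of the 12 points RAs explain names them

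*Combined protocol and SAP*

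**What the plan says.** Section 10.1.6 prescribes the assurance: "The RAs will assure each participant that their information will be kept confidential and not shared with anybody, including family members, in any context". Section 11.3 repeats it almost word for word: "The RA will assure each participant that their information will be kept confidential and not shared with anybody, including family members, in any context". Each section then lists data-handling points that the RA explains before data are collected.

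Section 11.4 takes a different position: "There are certain exceptions to this rule, as permitted by law and professional ethics". The first exception reads "We may disclose confidential information when we judge that there is a strong possibility of serious harm"; it covers harm to the participant or to another person, and applies when no safety plan can be agreed with the participant. The second covers disclosures pointing to abuse of a child, an elder or a vulnerable adult, where "we may be required to notify state authorities". The section adds: "Our experience is that these exceptions will arise infrequently".

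Two safety rules also bear on the wording. Section 7.3 covers a positive answer on "a questionnaire item that measures suicidal ideation or develops suicidal ideation during the intervention implementation phase, the RA will immediately contact the PI"; after that contact, help is arranged together with the field supervisor. Section 7.1 lists suicidal ideation among the adverse events that "will be reported in writing to the NIMH Program Officer according to pre-determined expectations and timeframes with the NIMH policy".

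**The concern.** The assurance is an instruction about what to say to participants, and it is absolute. A participant who hears it has been told that nothing they say can reach anyone else. Under section 11.4 that is not so.

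This matters because disclosure is the participant's choice. Section 7.3 lets participants skip questions on depression and suicidal ideation, so the protocol has them decide whether to answer on the strength of a promise that its own rules do not keep. Spoken wording carries particular weight here: section 2.1 describes the population as typically illiterate, and section 4.3 allows the consent form to be read aloud and signed by fingerprint. What is at stake is participant protection and trust in the field staff, not the treatment comparison.

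**Working it through.** The plan states no figure on this point, so the check sets the texts side by side and makes one count.

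1. *Scope of the assurance (10.1.6, 11.3).* It covers all of a participant's information, any recipient and any circumstance. Family members are given as an example of who is excluded, not as the boundary of the promise. One permitted disclosure is enough to make it untrue.

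2. *Permitted disclosures (11.4).* There are two. Serious harm: disclosure is allowed, and no recipient is named. Probable abuse: the possible recipient is state authorities. Both can arise from what a participant tells study staff. The assurance and section 11.4 cannot both be true.

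3. *Cross-references.* Neither 10.1.6 nor the assurance paragraph of 11.3 refers to 11.4. Section 11.4 says what the team may do; it does not tell RAs to inform participants of it.

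4. *Points RAs explain before data collection (10.1.6).* Counted by sentence: numeric codes; locked cabinet; cabinet key; data-entry computer; Box storage; folder access; de-identified analysis sets; storage of summary results; analysis by the PI; aggregate presentation; separate storage of questionnaires and identifiers; master list. Total 12; naming a limit on confidentiality, 0. The restriction on the master list is an access control, not a limit on the promise. Section 11.3 carries the same 12, so they are not added again.

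5. *Other places where the limits might appear.* The rest of 11.3 covers hair samples, de-identified archive sharing and the Certificate of Confidentiality. Section 4.3 lists the contents of the consent document, and 11.2 describes the verbal explanation. None mentions the harm or abuse exceptions.

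6. *Ideation and adverse events.* Under 7.3 the route runs from RA to PI to field supervisor, all within the study team. Under 7.2 adverse event data go to the Independent Safety Monitor (ISM), the IRB and the NIMH Program Officer. The report contents listed in 7.1 include a detailed account of the event and its effect on the participant, but the only identifying details they require are those of the research protocol. This is a tension with the assurance, not a contradiction.

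7. *How many hear it.* The assurance goes to each participant. The synopsis plans 226 adults. Section 9.1 expects families to average 2 to 4 adults, and 116 × 2 = 232 to 116 × 4 = 464. Section 4.1 also invites adults with PHQ-9 scores of 15 or above, who would hear it too, so 226 may be an undercount. The documents give no rate for serious-harm or abuse disclosures, so the number affected by an exception is not estimated.

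**The case against.** The strongest reply is that the protocol already handles this. Section 11.4 follows 11.3 in the same chapter, restates the general rule and then qualifies it. The sentences around the assurance concern private interviews and family sessions, so its evident purpose is to keep one relative's status from the others. The 12 points are introduced as privacy safeguards, and a list of safeguards would not be expected to include exceptions. The consent form may state the limits, and RAs can read it aloud, so literacy cuts both ways. The IRB approved the protocol, and the ISM reviews consent procedures before the study starts.

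Much of this stands as mitigation. It does not repair the sentence: staff who read both sections are still instructed to say something that the second section makes untrue, and the evident purpose does not narrow wording that reaches every context.

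Two stronger readings are tempting and are not supported. A reader might infer that participants are never told the limits. The consent form and RA manual were not available for this review, and the verbal explanation in 11.2 is described only in general terms, so that cannot be said. A reader might also infer that identifiable reports of suicidal ideation go to the ISM, the IRB and NIMH in breach of the promise. Nothing in 7.1 or 7.2 shows that participants are named in those reports.

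**Conclusion.** The assurance in 10.1.6 and 11.3 is untrue under section 11.4. This is a wrongly stated rule, not a missing detail. None of the 12 points that RAs explain corrects it. The conclusion rests on the wording alone and needs no assumption about the consent form: if that form states the limits, the spoken assurance contradicts it; if it does not, participants may not hear them at all. Whether anyone is in fact misled is unknown.

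The size is modest. The wording reaches every participant, the exceptions are expected to be rare, no number affected can be given, and the statistical analysis is unaffected. It should be corrected because the correction is cheap and bears on participant protection.

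**What to change.** In 10.1.6 and 11.3, keep the promise but replace its closing phrase (*in any context*) with: *except in the situations described in section 11.4 (risk of serious harm to self or others; suspected abuse that must be reported) and when the PI and field supervisor must be told so that they can help with a safety concern*. Add one plain spoken sentence giving these limits to the explanation RAs already make before collecting data. Check that the consent form and RA manual say the same. Leave the safety pathway unchanged.

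Do not substitute a promise that information stays within the study team. The team includes local interventionists (5.1) and field supervisors who are also community leaders and pastors (7.3), while 10.1.6 now restricts the cabinet key, study folders and master list to the PI. Such wording would loosen the present protection.

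The cost is two reworded paragraphs, a few minutes of the two-day RA training (10.1.1), and approval by the IRB (11.1) and the ISM (7.2). Some participants may disclose less once they know the limits; the documents give no basis for a number. The explanation is first given before baseline data are collected and randomization follows the baseline survey (4.3, 6.2.2), so any effect on screening or baseline answers cannot depend on the assigned arm.

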10.2 Data Management, Analysis, and Quality Assurance

Baseline and follow-up data will be entered into an Excel database and exported to SAS statistical package for analyses. Privacy and security rules will be applied to protect the confidentiality and security of the data. Security features will be applied at multiple levels, including the data element, user, application, and hosting services, with password protection for data access monitoring. These features will ensure control of access, authentication of users, and transmission security. The field team will be trained in project data maintenance.

10.2.1 Data Safety

Several precautions will be taken to minimize the unintended risk of disclosure of personal information. The protection of data for this study includes the following steps:

- Before conducting the fieldwork, the study protocol and survey measures will be submitted to the Institutional Review Board at the University of Massachusetts Amherst. The study will be initiated only after obtaining approval. All the study members will complete the Good Clinical Practice (GCP) and Collaborative Institutional Training Initiative (CITI) Course in the Protection of Human Research Subjects – online training in research ethics - to ensure that all personnel is compliant with confidentiality training.
- All information collected during the study will remain confidential. Interviewers will reassure participants that numerical codes would be used in place of names in all records to ensure confidentiality. The survey materials (questionnaires, transcriptions, and field notes) will be stored in a locked cabinet in the PI's office. Only the PI will have access to the cabinet's key. Data entry will be done on the PI's office computer (encrypted and password protected) under the full supervision of the PI. The original data will be kept on Box, a secure, networked UMass data storage system, after fieldwork. The folders will only be accessible by the PI through the on-campus network. De-identified data sets will be used for statistical analyses. Summary data and analysis results will be stored on the PI's UMass office computer or the Box network. The PI herself will do data analysis and documentation. Data presented will not include the names of any individuals. All information will be presented in aggregate form in the manuscript or conference abstract, and no individual respondent will be identified. The PI will take responsibility for destroying questionnaires and hard copies of study documents using a paper cutting machine five years after completing data analysis, documentation, and publication.
- Participant information, including name and contact information, will be collected on form separate form from study data at enrollment. Later, this information will be saved in a password-protected file on the PI's office computer. The study identification number or code number assigned to each participant will be retained in the data stored at UMass Amherst. All hard copies will be stored in the locked file cabinet in a locked office and electronic information on the PI's computer using an encrypted and password-protected file. Only the PI will have access to this information. The Master List linking participant ID numbers with identifying information will be destroyed after the completion of data analysis.
- All data stored in computer files will be encrypted and password protected.

- After the fieldwork, only one set of cleaned data set will be maintained. The file will be kept on a secure UMass data storage system. The folders will be accessible only by the PI through the on-campus network. Summary data and analysis results may be stored on the UMass office network M drive. These files will be removed from the network drive five years after the completion of data analysis, documentation, and publication.

10.2.2 Validity and Integrity

The PI and University of Massachusetts undergraduate RA will monitor the validity and integrity of the data on an on-going basis. The PI and RA will have online meetings every other week with the investigators, and alternate between online and in-person meetings every week with field-team members (community interventionist, field supervisors, and research assistants) throughout the data collection and intervention period, to review the accuracy, quality of the data, coding of data collected, monitoring of protocol, ongoing training, and problem-solving. The PI will meet regularly with the RA to ensure that data are processed appropriately. The study investigators will closely supervise the field-team to maintain quality.

10.2.3 Quality Control Procedures

This manual of operations and procedures has included details of the study procedures to ensure that procedures are implemented correctly and consistently to monitor intervention fidelity. Copies of this study manual will be kept at the University of Massachusetts Amherst, Vanderbilt University, Tennessee, and the study site. All field-team members will undergo thorough training regarding study procedures, including the Protection of Human Research Subjects and Good Clinical Practice. Retraining will be done as necessary.

Quality assurance of data entry consists of proactive tools that are implemented to increase the quality of data processing components. Specifically, these include form design to avoid missing; training of research assistants on the study forms so that they are familiar with the required responses; design of the data entry forms; specifications of the data fields to reflect the nature of the data to be entered; specification of the edit parameters and checking algorithms so that every area is verified as thoroughly as

possible; and validation of the database system to certify that data entered into the data entry screens are accurately recorded in the databases.

For data quality assurance measures, we will conduct training of the RAs on data collection techniques with periodic retraining and immediate review of data collection to be sure that data collection forms are fully complete.

For data quality control measures, we will conduct regular analyses to investigate: the number of missing data items; the number and type of forms that are failing edit; and the distribution of data to identify outliers.

